### 4.4.3 Electrocardiogram, Vital Signs and Physical Examination

The evaluation of electrocardiogram (ECG) and vital signs (including body temperature,

pulse rate, respiratory rate [RR], and supine Blood Pressure [BP]), will be summarized by visits and by treatment group.

#### 4.5 PHARMACOKINETICS ENDPOINTS

PK parameters will be calculated by non-compartmental methods from the BIO89-100 serum concentration data in Intensive PK subgroup, if the data are suitable.

- Maximal observed serum concentrations ( $C_{max}$ ) within a dosing interval
- Area under the serum drug concentration by time curve within a dosing interval ( $AUC_{0-\tau}$ )
- Time to achieve  $C_{max}$  ( $T_{max}$ )
- Terminal elimination half-life ( $t_{1/2}$ )
- Trough concentration

Additional PK parameters may be calculated if also deemed appropriate.

PK parameters will be calculated separately by designee of 89BIO.

Serum concentration and PK parameters data will be analyzed using the Pharmacokinetics Analysis Set.

#### 4.7 COVARIATES AND SUBGROUPS

- TG  $<750$  mg/dL or  $\geq 750$  mg/dL
- Background lipid medication (Yes, No)
- Type of background lipid medication (use of statin (including combo therapy), use of fibrate therapy, use of prescription fish oil, Ezetimibe, and Bempedoic acid), provided there is sufficient number of subjects in the subgroup
- Type 2 diabetes (Yes, No)
- Age categories (21-<65,  $\geq 65$ ).

- Sex (male, female)
- Baseline weight <median and  $\geq$  median
- Region (US vs EU)
- TG responder at Week 8 (responder, non-responder)
- Use of background insulin medication (Yes/No) for insulin analysis only

Note, if the percentage of subjects within a certain subgroup is less than 33% (i.e., less than 6 of 18 subjects) of the overall cohort, only descriptive analysis will be performed.

More details of the analyses repeated in the above subgroups are described in [Section 7.5.1](#).

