## 7 STATISTICAL METHODS OF ANALYSES

### 7.1 GENERAL CONSIDERATIONS

The statistical analysis for this study will be performed by combining the main cohort and the fibrate extension cohort. A single database lock will be implemented.

All the tables and figures will be based on the pooled data from both cohorts, unless otherwise specified. One set of listings will be generated for the whole study.

In general, summaries and analyses will be presented by dose/treatment group. Descriptive statistics will be presented for demographics and baseline characteristics, safety endpoints, and PK and PD parameters. Continuous variables will be summarized by number of subjects and mean, SD/standard error, median, minimum, and maximum values. Minimum

---

and maximum will be presented to the same number of decimal places as reported/collected. One additional decimal place will be presented for mean and median. Two additional decimal places will be presented for SD up to a max of three decimal places.

Categorical variables will be summarized by number and percentage of subjects. Percentage will be presented to one decimal place. The number of missing values will be presented as a separate category with no percentage, but only if 1 or more subjects are missing data for the summary. Otherwise, all categories will be presented (even if no subjects are counted in the category). Counts of zero in any category will be presented without percentage.

All statistical tests will be 2-sided and tested at a statistically significant level of 0.05 without adjustment for multiplicity. Confidence intervals will be 2-sided 95%, unless stated otherwise. Two-sided p-values will be presented with four decimal places and values less than 0.0001 will be presented as <.0001.

Both reported units (CN) and SI units will be presented in listings.

Both CN and SI units will be used in lipid panel (TG and other lipids) tables and figures.

For the rest, only CN units will be used for tables and figures, unless otherwise specified. Insulin will be presented with conventional unit of  $\mu$ IU/mL;

The listings will only present non-imputed data.

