### 7.5.1 Analysis of Primary Efficacy endpoints

The primary endpoint is the percent change in TG at Week 8 from baseline. The TG value at week 8 is defined as the average of TG values at [REDACTED]

[REDACTED] In case of missing TG value at [REDACTED] the non-missing result will be used as the week 8 TG. The primary efficacy analysis will be performed using a mixed model with repeated measure (MMRM). The model includes the treatment group, baseline TG values, background therapy use, visit, visit and treatment interaction. The model will be fitted using all planned visits up to Week 8.

If the mixed model assumption of the MMRM method is severely violated, the non-parametric van Elteren test stratified by baseline TG level and background lipid therapy will be used to test the treatment difference using the pooled data. The location shift estimate, and Hodges-Lehmann 2-tailed 95% confidence interval will be presented. For the comparison between the individual dose group and the placebo, the unstratified Wilcoxon rank-sum test will be used instead due to the low sample size.

The primary efficacy analysis will be repeated in the subgroups (as noted in [Section 4.7](#)).

[REDACTED]  
[REDACTED]  
[REDACTED]  
[REDACTED]

[REDACTED]  
[REDACTED]  
[REDACTED]

[REDACTED]

[REDACTED]

[REDACTED]

[REDACTED]

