### 7.5.2 Analysis of Secondary Efficacy Endpoints

Full analysis set will be used for all secondary efficacy analyses. The proportion of subjects with TG <500 mg/dL at Week 8 will be summarized by treatment group and analyzed using Cochran Mantel Haenszel (CMH) method stratified by the 2 stratification. Unstratified Chi-square test will be performed for comparisons between the placebo and the individual dose group or if the sample size within a stratum is too small (< 5 subjects). In addition, responder analysis at Week 8 will be performed to ensure the consistency of the results. The following threshold will be used to calculate: the proportion of subjects with TG normalized; with TG reduction by  $\geq 30\%$ ,  $\geq 40\%$ ,  $\geq 50\%$ ,  $\geq 60\%$ ,  $\geq 70\%$ ,  $\geq 80\%$ , and  $\geq 90\%$  from baseline.

Cumulative distribution function of both percentage changes from baseline and changes from baseline for TG at Week 8 by treatment group will be summarized descriptively and graphically.

Percentage change in VLDL-C, LDL-C, non-HDL-C, HDL-C, VLDL-TG, ApoB, hsCRP, fasting plasma glucose, adiponectin, and body weight from baseline to Week 8 will be analyzed similarly as the primary endpoints. For parameters that only have one post-baseline measurement, an ANCOVA model will be performed with treatment and background therapy as factors and baseline value as covariate.

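### The SAP lists TG response at Week 8 as a subgroup with no cut-off in 4.7 and no limit on use, so its visible text repeats the primary Week 8 TG analysis within strata defined by Week 8 TG

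*SAP*

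**What the plan says.** SAP 4.7 (Covariates and Subgroups) lists baseline TG level, background lipid medication and its type, type 2 diabetes, age, sex, baseline weight and region, and then "TG responder at Week 8 (responder, non-responder"). The last bullet is "Use of background insulin medication (Yes/No) for insulin analysis only". That entry carries a limit on use; the responder entry carries none, and 4.7 gives it no cut-off.

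A note in 4.7 sets a size rule. A subgroup holding under 33% of subjects, glossed as "less than 6 of 18 subjects) of the overall cohort, only descriptive analysis will be performed".

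The section then hands over to 7.5.1: "More details of the analyses repeated in the above subgroups are described in" that section. SAP 7.5.1 defines the primary endpoint as percent change in TG from baseline to Week 8 and states: "The primary efficacy analysis will be repeated in the subgroups" of 4.7. No exception is visible. Redacted lines follow directly.

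Several thresholds for Week 8 TG appear elsewhere:

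- SAP 7.5.2: "The proportion of subjects with TG <500 mg/dL at Week 8 will be summarized by treatment group", and further "the proportion of subjects with TG normalized; with TG reduction by" seven steps from 30% to 90%.
- SAP 7.5.3: a split at a 30% TG reduction, used for ALT, body weight, MRI-PDFF and a redacted item. It does not use the word responder or cite 4.7.
- Protocol 9.4.3: the word responder is attached to TG below 500 mg/dL.

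On pooling, SAP 7.1 says: "The statistical analysis for this study will be performed by combining the main cohort and the fibrate extension cohort".

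**The concern.** The other visible entries in the 4.7 list are demographic, baseline or background characteristics. TG response at Week 8 is computed from the same measurement that forms the primary endpoint. Splitting on it and then comparing arms on Week 8 TG change conditions on the outcome. Both arms are cut at the same value, so their means within each stratum are pulled together. In addition, a placebo subject who falls below the cut is not the counterpart of a treated subject who does. Randomisation no longer supports the comparison.

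What is at stake is interpretation of the subgroup output. A reader would see a much smaller difference in both responders and non-responders than in the whole trial, and could take it for a treatment effect. The size of that apparent effect would also depend on a cut-off that the visible text does not fix.

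**Working it through.** **Inputs** (SAP 3.5): mean percent change -50 on BIO89-100 and -5 on placebo, SD 40, 18 per arm, two-sided alpha 0.05, about 10% lost to follow-up. Planned sizes: main cohort 72 active and 18 placebo; fibrate cohort 18 and 18; pooled 72 + 18 = 90 active and 18 + 18 = 36 placebo. The cut-offs of 30% and 50% are assumptions, because 4.7 gives none.

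**The plan's own figure.** 18 less 10% is about 16 per arm. A two-sample t test for 45 points with SD 40 then has 86.8% power, which agrees with the stated figure of at least 86%.

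**Within-stratum means.** For a normal outcome with mean m and SD s, cut at c, let a = (c - m)/s. The responder probability is Φ(a), the responder mean is m - s·φ(a)/Φ(a), and the non-responder mean is m + s·φ(a)/(1 - Φ(a)).

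Example, 30% cut (c = -30):

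- Placebo: a = (-30 + 5)/40 = -0.625, Φ = 0.266, φ = 0.328. Responder mean -5 - 40 × 0.328/0.266 = -54.4; non-responder mean -5 + 40 × 0.328/0.734 = 12.9.
- Active: a = (-30 + 50)/40 = 0.5, Φ = 0.691, φ = 0.352. Responder mean -50 - 40 × 0.352/0.691 = -70.4; non-responder mean -50 + 40 × 0.352/0.309 = -4.4.

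| Cut | Stratum | Active | Placebo | Apparent difference (true: 45) |
|---|---|---|---|---|
| 30% | Responders | -70.4 | -54.4 | 16.0 |
| 30% | Non-responders | -4.4 | 12.9 | 17.2 |
| 50% | Responders | -81.9 | -70.0 | 11.9 |
| 50% | Non-responders | -18.1 | 4.7 | 22.8 |

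(Differences are taken before rounding.) Simulation gives the same values to within 0.1 point.

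**The size rule read on the overall cohort.** The responder share at 90:36 is (90 × 0.691 + 36 × 0.266)/126 = 57% at the 30% cut and (90 × 0.500 + 36 × 0.130)/126 = 39% at the 50% cut. With the main cohort alone (72:18) the shares are 61% and 43%. SAP 5.5 reports low fibrate enrolment, so the actual ratio probably lies between these. Both strata exceed 33% in each case and stay inferential. At a 60% cut the responder share at 90:36 is 31%, so that stratum would become descriptive.

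**The size rule read as 6 of 18 per arm.** At the 30% cut, expected placebo responders are 18 × 0.266 = 4.8 and expected active non-responders are 18 × (1 - 0.691) = 5.6. Each stratum therefore has one arm expected below 6, and both would be expected to be descriptive. At the 50% cut, placebo responders are 18 × 0.130 = 2.3, while non-responders number 9.0 active and 15.7 placebo; only the responder stratum would be descriptive.

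**Limits of the model.** It uses simple means, not the planned MMRM. It also puts Φ((-100 + 50)/40) = 10.6% of active subjects below -100%, which is impossible. With values floored at -100, the 30% cut gives 13.5 and 17.2 points. A cut at TG below 500 mg/dL was not modelled, because it is not one percentage: from a baseline of 600 mg/dL it needs 100 × (500/600 - 1) = -16.7%, and from 1000 mg/dL it needs -50%.

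**The case against.** The strongest objection is that the point turns on redacted text. The lines hidden in 7.5.1 come straight after the sentence on subgroups, where a definition or exclusion would naturally sit. Parts of 7.5.3 and the SAS code are also hidden, and the table shells are a separate document. This stands as a condition on the whole point. A reader might infer that the plan has no responder cut-off anywhere; the documents support only that 4.7 gives none and that no visible text defines the term.

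Second, 7.5.3 offers a sensible purpose: non-TG outcomes split at a 30% TG reduction. It is the only visible analysis within TG-response groups, and may well be what the bullet was for. However, no visible text links the two, and the literal instruction in 7.5.1 covers the bullet. A reader might also infer that 7.5.3 itself compares arms within those groups. Its visible wording does not say so; it could equally mean comparing the two response groups with each other.

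Third, the size rule may already restrain the output. On the per-arm reading at a 30% cut it would be expected to make both strata descriptive. A reader might conclude that the rule plainly fails, but that holds only on the overall-cohort reading. What remains is that its two wordings give different answers and that neither removes the output.

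Finally, the magnitudes depend on assumed cut-offs and a simplified model. They are illustrations, not predictions.

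**Conclusion.** The point holds, conditionally. On the visible text, the SAP repeats the primary Week 8 TG analysis within strata defined by Week 8 TG. That is a wrong rule for this entry and not only a missing detail, unless the redacted lines of 7.5.1 exclude it. Under the planning assumptions the 45-point difference would shrink to between about 12 and 23 points within strata, depending on the cut.

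A reader might infer that the trial's main conclusion is compromised. The documents do not support that: the primary comparison in the Full Analysis Set, its power and the success rule in SAP 7.5 do not use this subgroup. Nor do they show that such a table has been laid out. The consequence is confined to one subgroup output that could be misread, so the priority is low.

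**What to change.** Either delete the responder bullet from 4.7, or define it and limit it as the insulin bullet is limited, for example: *TG reduction from baseline at Week 8 <30% vs ≥30%, for Section 7.5.3 analyses only*. In 7.5.1, state that the primary TG analysis is repeated only in subgroups fixed before first dose. If 7.5.3 includes comparisons between arms within TG-response groups, label them as associations, since the groups are formed after randomisation. If the redacted text already contains this limit, repeat it in 4.7.

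The cost is one deleted or qualified bullet and a few words in 7.5.1. Any output of TG change by TG response would be dropped; the 7.5.3 models stay.

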## 5 DEFINITIONS

### 5.1 BASELINE DEFINITION

In general, baseline will be defined as the most recent non-missing measurement (scheduled or unscheduled) prior to the administration of the first dose of IP. For numerical measurements that have duplicates or triplicates (for the same visit), the arithmetic mean will be used. Some measurements have special definitions of baseline, which are defined below.

The mean TG value will be used for stratification factor [REDACTED]

Baseline Triglyceride is defined as the average of [REDACTED] and the preceding two lipid-qualifying visits collected in EDC. Fasting status is required for the TG values to be included.

The definition of baseline of other lipid panel labs is the average of last two non-missing screening fasting values and [REDACTED] value (Pre-dose, fasting).

The definition of baseline vital signs is the average of the last two non-missing screening values and [REDACTED]. If there is Case Report Form (CRF) average value on duplicate measurements of BP and/or Pulse on [REDACTED], only the individual values will be included in the baseline derivation.

The baseline definition for MRI for subjects of the main cohort is the [REDACTED] value. The baseline definition for MRI for subjects of the fibrate expansion cohort is the value obtained between [REDACTED]

The baseline definition for safety numeric measurements (except for liver tests) is the average of last two non-missing screening values and [REDACTED]

The baseline definition of PK is the [REDACTED]. The details will be described in a

separate document.

## 5.2 ACTUAL TREATMENT GROUP

[REDACTED]

## 5.3 STUDY DAY

The day a subject receives their first dose of investigational product will be considered as

[REDACTED]

If a subject is randomized but never dosed, study day will be calculated using the randomization date and randomization date will be set to [REDACTED]

If date of interest occurring on or after the relative date, relative day is calculated as: date of interest – relative date + 1, else if date of interest occurring prior the relative date, relative day is calculated as: date of interest – relative date. Data will be presented on listings in order of site number/subject number, assessment date and assessment (in order collected on CRF, unless specified otherwise). Dates will be presented in the format of YYYY-MM-DD.

For subjects with study interruptions due to COVID-19, post-interruption study day will be calculated as: (Index date) – (the date of [REDACTED] + 1 – (the interruption duration as defined in the study interruption CRF). Visits post-interruption due to COVID-19 will use this corrected study day for visit windowing.

## 5.4 END OF STUDY

A subject is considered to have completed the study if the subject has completed all phases of the study including the last scheduled procedure shown in [Table 6](#). The EOS is defined as the date of the last visit of the last subject in the study.

## 5.5 STUDY SCOPE

For the efficacy analysis of the primary endpoint, results will be presented in two different formats as shown below:

1. A comparison between the pooled BIO89-100 group and the pooled Placebo group.

Subjects across all BIO89-100 dose groups will be pooled together to compare with all the placebo subjects. The table header is shown below ([Table 2](#)). The Total group will be presented as appropriate.

**Table 2. Table Header for Pooled Analysis**

<Description>	Placebo QW	BIO89-100	Total
---------------	------------	-----------	-------

	Pooled	Pooled	
--	--------	--------	--

2. A comparison between individual BIO89-100 dose group and the placebo group.

Each BIO89-100 dose group will be compared with the placebo group. Due to the low number of subjects enrolled in the fibrate cohort, subjects randomized to BIO89-100 in fibrate cohort will be combined with the 27mg QW main cohort as the pooled 27mg QW group. The subjects randomized to placebo in the fibrate cohort will be combined with the placebo group. The table header is shown below (Table 3). The Total group will be presented as appropriate.

**Table 3. Table Header for Individual Dose Group Analysis**

<Description>	Placebo QW Pooled	BIO89-100 9 mg QW	BIO89-100 18 mg QW	BIO89-100 27 mg QW Pooled	BIO89-100 36 mg Q2W	Total
---------------	----------------------	----------------------	-----------------------	---------------------------------	------------------------	-------

For all other analyses, the results will be presented in a combined format as shown below (Table 3-1):

**Table 4-1. Table Header for All Other Analysis**

<Description>	Placebo QW Pooled	BIO89-100 pooled	BIO89-100 9 mg QW	BIO89-100 18 mg QW	BIO89-100 27 mg QW Pooled	BIO89-100 36 mg Q2W	Total
---------------	-------------------------	---------------------	----------------------	-----------------------	---------------------------------	---------------------------	-------

## 5.6 PRE-TREATMENT MEDICATION AND PRE-TREATMENT PROCEDURES

Any medication/procedure that starts and stops prior to [REDACTED].

## 5.7 BASELINE MEDICATION

Medications that have [REDACTED] within the duration of exposure will be considered baseline medications, i.e., medication taken prior to and/or on [REDACTED] and ongoing/stopped after [REDACTED].

## 5.8 CONCOMITANT MEDICATION AND CONCOMITANT PROCEDURES

Any medication/procedure that is taken any day on or after [REDACTED] is considered as concomitant medication/procedure. This includes medications/procedures that were started prior to administration of first dose and that were continued to be taken after [REDACTED].

## 5.9 ADVERSE EVENT AND SERIOUS ADVERSE EVENT

An AE is any untoward medical occurrence in a clinical study subject, temporally associated with the use of investigational product, whether or not considered as related to the investigational product. An AE can, therefore, be any unfavorable and unintended sign (including an abnormal laboratory finding), symptom, or disease (new or exacerbated) temporally associated with the use of investigational product.

A Serious Adverse Events (SAE) is defined as any untoward medical occurrence that, at any dose 1) results in death; 2) is life-threatening; 3) requires inpatient hospitalization or prolongation of existing hospitalization; 4) results in persistent disability/incapacity; 5) is a congenital anomaly/birth defect; 6) medically or scientifically judged as serious in other situations.

## 5.10 TREATMENT EMERGENT ADVERSE EVENT

TEAEs are AEs with onset date and time after or identical to the date and time of the first dose of the investigational product until the last dose + 28 days.

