<sup>a The actual doses will be  $\pm 5\%$  of the mg dose due to technical considerations related to drug withdrawal from the vials into the syringes for injection. This difference is considered negligible for subject exposure.

The study includes lifestyle stabilization, TG qualification, treatment, and follow-up periods.

Screening period: ~6 to 9 weeks

Lifestyle stabilization ~4 weeks (minimum) to ~6 weeks (maximum)

period:

(~6 weeks for subjects stopping lipid-altering therapy, ~4 weeks for

subjects already on stable, protocol accepted, lipid-altering therapy)

TG qualification

period

~2 weeks to ~3 weeks

Treatment period 8 weeks

Follow-up period 4 weeks

**Data monitoring committee:** No data monitoring committee is planned for this study.

Figure 1: Study Schema: Main Cohort

[figure not shown]
[figure not shown]

Figure 2: Study Schema: Fibrate Expansion Cohort

Abbreviations: EOT = end of treatment, EOS =end of study, N = number of subjects, QW = once weekly. Q2W = every 2 weeks, TG = triglyceride, V = visit, wk = week.

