#### 8.3.1. Time Period and Frequency for Collecting AE and SAE Information

The timing and frequency of collection of all AEs and SAEs is specified in the SoA (Table 2).

Table 4 summarizes the different reporting periods for AEs, SAEs and events to monitor. Events to monitor are defined in Section 10.3.3.

**Table 4:** Adverse Event Reporting Periods

| Type of
Event                   | Adverse Event   | Serious Adverse Event   | Events to Monitor with Investigational Product                     |
|------------------------------------|---|---|---|
| Reporting period                   | From consent until 28 days after last dose of investigational product | From consent until 28 days after the last dose of investigational product | From consent until 28 days after the last dose of investigational product |
| Reporting
Timelines to
89bio | Entered into the clinical database on an ongoing basis                | Within 24 hours   | Within 24 hours   |

All SAEs will be recorded and reported to 89bio or designee immediately and under no circumstance should this exceed 24 hours, as indicated in Appendix 3 (Section 10.3). The

Investigator will submit any updated SAE data to 89bio or designee within 24 hours of it being available.

Investigators are not obligated to actively seek AEs or SAEs after conclusion of the study participation. However, if the Investigator learns of any SAE, including a death, at any time after a subject has been discharged from the study, and he/she considers the event to be reasonably related to the IP or study participation, the Investigator must promptly notify 89bio or designee.

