#### **Assessment of Intensity**

The severity of each AE will be assessed at onset by a nurse and/or physician. When recording the outcome of the AE the maximum severity of the AE experienced will also be recorded. The severity of the AE will be graded according to the CTCAE v5.0:

**Grade 1:** Mild; asymptomatic or mild symptoms; clinical or diagnostic observations only; intervention not indicated.

**Grade 2:** Moderate; minimal, local, or non-invasive intervention indicated; limiting age-appropriate instrumental Activities of Daily Living (ADL)\*.

**Grade 3:** Severe or medically significant but not immediately life-threatening; hospitalization or prolongation of hospitalization indicated; disabling; limiting self-care ADL\*\*.

**Grade 4:** Life-threatening consequences; urgent intervention indicated.

**Grade 5:** Death related to AE.

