## 4.4 SAFETY ENDPOINTS

### 4.4.1 Adverse Events

The evaluation of adverse events (AE) will include only incidence of treatment-emergent AEs (TEAEs), defined as AEs with onset date and time after or identical to the date and time of the first dose of the investigational product until the last dose + 28 days or continuing AEs that worsen the grade post IP. When onset time is missing or partial missing, AE occurs on the same day as first dose date are considered as TEAE. The frequency of TEAEs, treatment-emergent serious AEs (TESAEs), and number of subjects who discontinue due to TEAEs will be summarized.

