### 7.6.1 Adverse Events

Subject incidence of TEAEs will be tabulated by Medical Dictionary for Regulatory Activities (MedDRA, Version 23.0) system organ class, MedDRA preferred term, and

treatment groups. All TEAEs, all treatment-emergent related AEs, all TESAEs, and all treatment-emergent serious related AEs, the most severe CTCAE grade, TEAEs leading to IP discontinuation, and TESAEs leading to IP discontinuation will be summarized. Related is defined as “possibly related”, “probably related”, or “definitely related” to randomized investigational medicinal product. Subjects will be counted only once within a SOC and Preferred Term (PT), even if the subject experienced more than one TEAE within a specific SOC and PT, and PT only.

All AEs, TESAEs, TEAEs leading to IP discontinuation, Fatal TEAEs and COVID-19 related AEs will be listed.

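### SAP 4.4.1 and SAP 5.10 define TEAEs differently; if 5.10 is the one programmed, adverse events already open at first dose that worsen on treatment drop out of the TEAE tables

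*SAP*

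**What the plan says.** **SAP 4.4.1 (Adverse Events, under Safety Endpoints).** TEAEs are "defined as AEs with onset date and time after or identical to the date and time of the first dose of the investigational product", up to 28 days after the last dose. The same sentence adds a second route into the set: "or continuing AEs that worsen the grade post IP". The next sentence deals with incomplete times: "When onset time is missing or partial missing, AE occurs on the same day as first dose date are considered as TEAE".

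**SAP 5.10 (Treatment Emergent Adverse Event, under Definitions).** "TEAEs are AEs with onset date and time after or identical to the date and time of the first dose of the investigational product", again up to 28 days after the last dose. The section ends there. It has neither the worsening route nor the rule for a missing onset time.

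**SAP 7.6.1 (Adverse Events, under Safety Analysis).** "Subject incidence of TEAEs will be tabulated by Medical Dictionary for Regulatory Activities" terms, by treatment group. It also calls for summaries of related, serious and most-severe-grade events and of events leading to discontinuation of investigational product. It cites neither definition.

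**Protocol.** The available text uses the term TEAE in its objectives and in section 9.4.5 but does not define it. Table 4 in section 8.3.1 sets the AE reporting period as "From consent until 28 days after last dose of investigational product".

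**The concern.** A programmer who follows 5.10 and one who follows 4.4.1 would build different TEAE datasets from the same plan, and nothing visible says which of them is right.

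The events at issue are AEs that begin during screening, are still open at first dose, and then worsen. Section 4.4.1 counts them and 5.10 does not. An event that was mild in screening and became severe or serious on treatment would be missing, under 5.10, from every summary that uses the treatment-emergent flag. TEAE frequency, TESAE frequency and discontinuations due to TEAEs are the first-listed safety endpoints. The groups are small, there is no data monitoring committee, and protocol 4.2 says the results will inform dose selection for Phase 3. A single subject can be the whole count for a preferred term.

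**Working it through.** The plan states no figure to reproduce. The check compares the two texts and then scales the difference.

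**1. The two rules side by side**

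| Event | SAP 4.4.1 | SAP 5.10 |
|---|---|---|
| Onset at or after first dose, within 28 days of last dose | TEAE | TEAE |
| Onset before first dose, ongoing, worsens in grade after dosing | TEAE | Not a TEAE |
| Onset on the day of first dose, time missing or partial | TEAE | No rule given |

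Everything that 5.10 counts is also counted by 4.4.1, and the reverse does not hold. So the count in any arm under 5.10 is equal to or lower than the count under 4.4.1.

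**2. Can such events occur?**

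- AEs are collected from consent (protocol Table 4), and the schedule marks AE collection at screening visits.
- The time before dosing is not short: "Screening period: ~6 to 9 weeks" (protocol, Intervention Groups and Duration).
- On severity, the protocol has it assessed at onset, and then: "When recording the outcome of the AE the maximum severity of the AE experienced will also be recorded" (Assessment of Intensity). No available text tells the site to open a new record, with a new onset date, when an ongoing AE worsens. Handled this way, the event keeps its pre-dose onset date and falls outside 5.10.

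Such events are therefore possible. The documents give no rate for them.

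**3. Where the event would still appear**

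SAP 7.6.1 lists all AEs, not only TEAEs, so the event would remain in the by-subject listing. It would be absent from the TEAE, TESAE and most-severe-grade summaries.

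**4. Scale**

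SAP 7.6.1 counts each subject once per system organ class and preferred term. Incidence in a row therefore moves only when the lost event was that subject's sole qualifying event in that row. The step per such subject is 1/n.

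| Column (planned size) | n | 1 subject | 2 subjects |
|---|---|---|---|
| 9 mg QW, 18 mg QW or 36 mg Q2W | 18 | 1/18 = 5.6 points | 2/18 = 11.1 points |
| Pooled placebo or pooled 27 mg QW | 18 + 18 = 36 | 1/36 = 2.8 points | 2/36 = 5.6 points |
| Pooled BIO89-100 | 4 × 18 + 18 = 90 | 1/90 = 1.1 points | 2/90 = 2.2 points |

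SAP 5.5 reports low enrolment in the fibrate cohort. If the pooled placebo and 27 mg groups end up between 18 and 36 subjects, their one-subject step lies between 2.8 and 5.6 points. The range of 0 to 2 affected subjects is an assumption for illustration. At 0 there is no shortfall.

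**The case against.** The strongest reply is that 5.10 is only a shortened restatement. Section 4.4.1 also presents itself as a definition, sits with the safety endpoints, and is the fuller text. If the programmers use it, nothing is lost. The sample code is redacted and the table shells are a separate document, so neither can show which rule is used. This stands as a limit: the undercount is conditional. It does not remove the contradiction, because 5.10 sits in the Definitions section and no visible text ranks the two.

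A second reply is that worsening is often captured anyway. Protocol Appendix 3 treats exacerbation of a pre-existing condition as an AE in its own right, and SAP 5.9 covers exacerbated disease. Worsening of a medical-history condition may therefore be entered with a post-dose onset, which 5.10 counts. This also stands, and it confines the gap mainly to AEs already open at first dose.

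A reader might draw four stronger conclusions that the documents do not support:

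- *TEAE counts will be too low.* This follows only if 5.10 is programmed and at least one such event occurs. Neither is known.
- *Toxicity can only be understated.* That is true of the count within an arm. The omission applies to placebo as well, so a lost placebo event would raise the drug-placebo difference.
- *Each lost event costs 5.6 points.* That holds only for a subject's sole qualifying event in a row, in a group of 18. The pooled columns move by less.
- *The event vanishes from the report.* It stays in the all-AE listing, and SAEs are reported to the sponsor separately within 24 hours.

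**Conclusion.** The inconsistency is real and should be corrected. Sections 4.4.1 and 5.10 give different sets of TEAEs, and nothing visible says which set 7.6.1 tabulates.

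The consequence is conditional. It requires that 5.10 is applied and that an AE open at first dose worsens while keeping its pre-dose onset date. In that case TEAE, TESAE and maximum-grade counts within each arm are equal to or lower than under 4.4.1. The direction of any change in the between-arm comparison depends on which arms the events fall in. The size cannot be obtained from the documents and may be nil. The one-subject steps of 5.6 and 2.8 points show how sensitive groups of this size are, and they do not estimate a shortfall.

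**What to change.** Replace the text of SAP 5.10 with the complete 4.4.1 definition, keeping all three parts:

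1. onset at or after first dose, up to 28 days after last dose;
2. or an AE continuing from before first dose that worsens in grade after investigational product;
3. with an AE on the day of first dose counted as treatment-emergent when its onset time is missing or partial.

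Have 4.4.1 and 7.6.1 refer to that single definition. A shorter paraphrase that left out the 28-day limit or the missing-time rule would create a third version.

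The cost is a small text edit and a check of the derivation code. That check should confirm that the CRF data allow post-dose worsening to be identified. The visible protocol text records severity at onset and maximum severity, but shows no date for a change of grade. TEAE counts may rise slightly compared with 5.10. Trial conduct and dosing are unaffected.
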